21 Sociodemographics (age, educational attainment, marital status, health insurance status); (b)
22 Medical/pregnancy history (height/weight, self-reported pre-pregnancy weight, weeks pregnant,
23 history of complications in prior pregnancies; (c) Smoking history (age started smoking, pre-
24 pregnancy time to first cigarette/cigarettes per day, past week time to first cigarette/cigarettes per
25 day, number of quit attempts before/during the current pregnancy, number of other smokers in
26 the household, rules about smoking in the household, nicotine dependence⁹²); (d) Smoking
27 timeline follow-back (to characterize daily smoking rates and/or use of alternative tobacco
28 products or nicotine replacement therapy since learning of the current pregnancy⁹³); (e) Smoking
29 attitudes (motivation to stop, confidence in ability to stop, intention to quit before the baby is
30 born, intention to remain abstinent after the baby is born, perceived stress levels); (f) Maternal
31 health/executive functioning (lifetime history of depression, general psychiatric symptoms,⁹⁴
32 current depressive symptoms,⁹⁵ discounting of delayed hypothetical monetary rewards,⁹⁶
33 behavioral economic measure of the reinforcing value of cigarettes,^{68,97} Behavior Rating
34 Inventory of Executive Function®-Adult Form [BRIEF-A; see attached], EQ-5D Health-Related
35 Quality of Life Questionnaire [see attached]); (g) Stressful life events (SAMHSA Life Events
36 Checklist [see attached]). Appropriately modified versions of these measures will be
37 administered at the other six formal assessments identified above. In addition, at the postpartum
38 assessments we will assess breastfeeding, including initiation, duration, and different levels of
39 breastfeeding (e.g., exclusive, predominant, any).
40

41 After participants' consent to join the study, we will collect contact information over the phone
42 including their mailing address (to send them equipment), as well as the phone number for an
43 alternative contact in the case that we are unable to reach the participant. We will also ask the
44 participant to tell us how we should describe their involvement in the research study should we
45 need to reach out to their alternative contact at some point. This form is attached, and it will be

1 updated following each formal assessment. Keeping an updated mailing address is important in
2 case participants need additional equipment or paperwork mailed to them.

3

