30 including: (a) features of the intervention that they felt facilitated or hindered engagement (e.g.,
31 technical difficulties/availability of technical support, self-monitoring using the CO monitor,
32 appropriateness of staff counseling surrounding smoking), (b) social/environmental variables
33 (e.g., quit support from friends/family, rules about smoking in the home, exposure to smoke-free
34 environments, social networks that promoted or discouraged quitting smoking) and (c)
35 internal/psychological variables (e.g., stress, psychological well-being, motivation to quit, self-
36 efficacy for quitting smoking). The semi-structured interview used to examine barriers and
37 facilitators of treatment engagement will use scripted prompts, however participants will be able
38 to respond freely and openly to each question. Their responses may be transcribed verbatim by
39 the research staff completing the interviews, or participants may type them into open-ended text
40 boxes.

41 42 STATISTICAL CONSIDERATIONS

43 44 Statistical Methods

45 Study conditions will be compared on baseline demographics and other characteristics using
46 analysis of variance (ANOVA) for continuous variables and chi-square tests for categorical

1 variables. If a specific characteristic differs significantly across study conditions and is
2 predictive of the outcome, it will be considered as a potential covariate in subsequent analyses.
3 Analyses of treatment effects on smoking status will adhere to an intent-to-treat approach¹⁰⁰
4 whereby all women randomized to each study condition will be included in the analyses
5 independent of early dropout, noncompliance, etc., with the exception of women excluded for
6 abortion/fetal demise as is convention in this research area. Cochran-Mantel-Haenszel tests (C-
7 M-H) will be performed for comparisons between the best practices plus incentives vs. best
8 practices alone conditions on point-prevalence smoking abstinence at the end-of-pregnancy and
9 6-months postpartum assessments. Comparisons of point-prevalence abstinence rates between
10 treatment conditions across all assessments through six months postpartum will be analyzed
11 using mixed model repeated measures for categorical data based on generalized estimating
12 equations (GEE) using a logistic link function (SAS: PROC GENMOD, SAS Institute, Cary,
13 NC). The two treatment groups will also be compared on breastfeeding and other measures

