20 currently maintained on opioid maintenance therapy. The only criteria for withdrawing someone
21 from the trial following randomization to treatment condition will be pregnancy termination or
22 fetal demise prior to participants' late-pregnancy smoking assessment (≥ 28 weeks gestation).
23 Women who fail to complete an orientation session or provide an initial CO sample indicating
24 that they are smokers will be withdrawn prior to randomization. Criteria will be assessed during
25 an initial eligibility screen that can be conducted either online or by phone to determine
26 preliminary eligibility and further evaluated during the formal intake assessment.
27

28 **Inclusion of Minorities and Women**

29 This project will include only women. Smoking among pregnant and newly postpartum women
30 has sufficiently special circumstances regarding the potential toxicity to the fetus and newborn,
31 the reasons for trying to quit smoking and prevent relapse, and the patterns of smoking reduction,
32 cessation, and relapse that they need to be studied exclusively in women.
33

34 Additionally, the project will include only Alaska Native women. However, should we receive
35 referrals from non-Alaska Native women in Alaska who are pregnant and currently smoking, we
36 will refer them to the Alaska tobacco quit line.
37

38 **Recruitment**

39 As in prior and current trials conducted at UVM, including the ongoing parent trial, applicants
40 will be recruited from online media advertisements. The text for these ads, as well as exemplars
41 of pictures, are attached to this submission. These ads were developed based on prior research
42 conducted by the ANTHC involving online recruitment of Alaska Native women. These ads will
43 include a link to the preliminary screening questions administered through REDCap. If eligible,
44 we will collect the participant's contact information and schedule a time to contact them to
45 provide more information about the study and conduct the consent phone call if they choose to
46 enroll.

1
2
3
4

FINANCIAL CONSIDERATIONS

5

Expense to Subject

6 No known expense to subject aside from their time.
7

8

Payment for Participation

9 Women in both conditions will receive compensation for completing 7 formal assessments at
10 \$50/assessment = \$350. Women assigned to the best practices plus incentives condition will
11 have the potential to earn incentives in the form of money loaded onto a PEX Debit Card for

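### No model is named for continuous postpartum measures, and the plan's only general covariate rule would almost always leave out a measure's own intake score, giving up precision at no saving

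*Combined protocol and SAP*

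**What the plan says.** All references are to the combined protocol and SAP.

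- **Comparison planned.** Statistical Methods: "The two treatment groups will also be compared on breastfeeding and other measures" collected postpartum. The measures beyond breastfeeding are not listed. PROC GENMOD is named for dichotomous outcomes. ANOVA is named for baseline comparisons and for the Treatment Acceptability Questionnaire (TAQ) items. Nothing is named for a continuous scale repeated postpartum.
- **Covariate rule.** Statistical Methods opens with baseline testing: "Study conditions will be compared on baseline demographics and other characteristics using" ANOVA or chi-square. It continues: "If a specific characteristic differs significantly across study conditions and is" also "predictive of the outcome, it will be considered as a potential covariate in subsequent analyses". The TAQ paragraph repeats the idea that characteristics differing between arms may become covariates.
- **Data available.** Assessment Battery lists, at intake, "current depressive symptoms", general psychiatric symptoms, delay discounting, BRIEF-A and EQ-5D. It then says: "Appropriately modified versions of these measures will be" "administered at the other six formal assessments identified above". Those six include 4, 8, 12 and 24 weeks postpartum.
- **Timing and cost.** The intake assessment is used to settle eligibility, so it precedes randomisation. It is one of the seven paid assessments under Payment for Participation.

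No section specifies the intake value as a covariate, a change score, ANCOVA or a longitudinal model for a continuous measure.

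**The concern.** Randomisation makes baseline differences a matter of chance, so a 5% test of baseline difference picks out a covariate about 5% of the time however strongly it predicts the outcome. What makes a covariate worth including is its correlation with the outcome, not the size of the chance imbalance. The first condition of the rule therefore discards nearly all the benefit that the second condition is meant to find.

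The stake is the precision of the postpartum comparisons on continuous scales. Among the background results in the Purpose section, incentives reduced postpartum depressive symptoms in depression-prone women, and Assessment Procedures says similar questionnaires are used so that results can be compared with prior trials. With 60 women these comparisons are imprecise to begin with.

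**Working it through.** The plan gives no SD, effect size, power or dropout figure for any continuous postpartum measure, so it has no figure of its own to reproduce.

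**Inputs.** From the documents: 30 women per arm (opening summary) and alpha 0.05 (Statistical Methods). Assumed: two-sided testing, equal SD at intake and postpartum, one postpartum visit, complete data, and r from 0.1 to 0.7. Differences are in SD units.

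**Step 1: gap needed at baseline.** The standard error of a difference in means is √(2/30) = 0.258 SD. With 58 degrees of freedom the critical t is about 2.00, so the gap must reach 2.00 × 0.258 ≈ 0.52 SD.

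**Step 2: how often the rule admits the intake score.** The first condition is met 5% of the time by construction; the second lowers that further. Simulating both conditions (40,000 trials per setting) gave:

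| r | Intake score admitted |
|---|---|
| 0.1 | 0.5% |
| 0.3 | 3% |
| 0.5 | 5% |
| 0.7 | 5% |

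The simulation adjusted whenever both conditions were met. The plan says only that the covariate is considered, so these are upper figures.

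**Step 3: precision if the intake score is always included.** The residual variance is multiplied by (1 − r²). Chance imbalance in the covariate costs a factor 1 + 1/(60 − 4) = 1.018, and one degree of freedom is lost. The confidence-interval width ratio is about √[(1 − r²) × 1.018]. For example, at r = 0.5 it is √(0.75 × 1.018) = 0.874. Detectable differences and power use the noncentral t distribution.

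| r | CI width vs unadjusted | Detectable at 80% power | Power at 0.5 SD |
|---|---|---|---|
| Unadjusted | 1.00 | 0.736 SD | 48% |
| 0.1 | 1.004 | 0.739 SD | 48% (47.5% vs 47.8%) |
| 0.3 | 0.963 | 0.708 SD | 51% |
| 0.5 | 0.874 | 0.643 SD | 59% |
| 0.7 | 0.721 | 0.530 SD | 75% |

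Break-even on variance is where (1 − r²) × 57/56 = 1, so r² = 1/57 and r ≈ 0.13.

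**Step 4: the rule as written against always adjusting (simulation).**

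| r | Power at 0.5 SD: rule / always | SD of estimate: rule / always | Type I error: rule / always |
|---|---|---|---|
| 0.3 | 48% / 51% | 0.25 / 0.25 | 0.048 / 0.050 |
| 0.5 | 49% / 59% | 0.25 / 0.225 | 0.044 / 0.050 |
| 0.7 | 49% / 75% | 0.24 / 0.19 | 0.035 / 0.051 |

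The rule behaves almost like no adjustment, and is somewhat conservative at higher r.

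**Step 5: effect of a typical chance gap.** The mean absolute baseline gap is √(2/π) × 0.258 ≈ 0.21 SD. At r = 0.6 it moves the unadjusted postpartum difference by 0.6 × 0.21 ≈ 0.12 SD.

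**Sensitivity.** With an assumed 20% dropout (24 per arm), the detectable difference is 0.83 SD unadjusted and 0.72 SD adjusted at r = 0.5. The pattern is unchanged.

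**The case against.** **The plan does not choose an unadjusted analysis.** A reader might infer that it prescribes ANOVA without intake scores for these scales. It does not: ANOVA is tied to baseline comparisons and TAQ items, and the method for continuous postpartum measures is simply unstated. Nor does the rule expressly bar other covariates. This stands as a limit on attribution. The point rests on the only general covariate rule, which is worded to cover subsequent analyses, together with that silence.

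**The scales are inferred.** Only breastfeeding is named among the measures to be compared. That depressive symptoms, EQ-5D and the rest are included is a reasonable reading of the repeated battery, but it is a reading.

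**The correlation may be low.** Intake is at 25 weeks' gestation or earlier, delivery intervenes, and follow-up runs to 24 weeks postpartum. Later instruments are modified versions, so the same score may not exist at both times. This stands: the range must reach down to r = 0.1, where there is no gain, and the fix must be confined to measures scored the same way.

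**Imbalance is not an added bias.** A reader might infer that a non-significant gap of 0.5 SD, shifting the result by 0.6 × 0.5 = 0.3 SD, is a separate harm. That gap lies at the edge of significance. The typical shift is about 0.12 SD, and the unadjusted confidence interval already allows for such variation.

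**It is an exploratory pilot.** No primary result changes. This stands, and bears on priority rather than on whether the change is worth making.

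**Conclusion.** The point holds in a limited form. Followed as written, the rule leaves a prognostic intake score out of about 95% or more of randomised trials, so the continuous postpartum comparisons are in effect unadjusted. How much is lost depends on a correlation that the documents do not give: nothing below about r = 0.13, little at 0.3, and a worthwhile amount from about 0.5 upward. These sizes apply to a single visit with complete data; no gain was computed for a multi-visit model.

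The documents do not support saying that the plan deliberately rejects intake scores, or that its estimates are biased. Nor does the point reach the abstinence outcomes, which are binary in women who all start as smokers, or breastfeeding and TAQ items, which have no intake value. It is an inexpensive improvement to secondary analyses.

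**What to change.** In Statistical Methods:

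1. List the continuous measures to be compared postpartum, and confirm for each that the same score exists at intake and at follow-up.
2. For each of those, state that its own intake score is always included as a covariate, whatever the baseline comparison shows. Use either ANCOVA at one named postpartum visit, or a repeated-measures linear model over the postpartum visits with one named between-arm contrast.
3. Stop using baseline significance tests to select covariates for these measures. The baseline table can remain as description.

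The covariate costs one degree of freedom per model. A repeated-measures model spends more on visit and arm-by-visit terms; ANCOVA at a single visit does not. No new data are needed, since intake is already collected and paid for. If r turns out to be near 0.1, the loss is under one percentage point of power.

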27 to protect against relapse once an initial period of abstinence has been achieved.⁸⁹
28

29 Following the initial quit week during which participants submit twice daily breath CO samples,
30 the schedule of monitoring will be reduced and saliva cotinine will be used to determine smoking
31 status. Only tests where the display indicates negative samples will result in participants earning
32 reinforcement. Specifically, during weeks two through six, participants will submit videos of
33 themselves completing saliva cotinine tests twice per week, then once per week from week seven
34 until delivery. During the once per week phase, the specific day on which participants are
35 required to submit a sample will be determined quasi-randomly (at least two days apart). The
36 sample will be prompted electronically via a text message at the start of the day and the
37 participant will have up to eight hours to provide the sample. This provides a balance between a
38 schedule that is sufficiently unpredictable that participants who are no longer abstinent may be
39 detected, while at the same time providing them with a reasonable time frame to submit a sample
40 upon being prompted to do so. The schedule of potential earnings during weeks two until
41 delivery will be a continuation of the escalating pay schedule from the initial quit week.
42 Importantly, intermittent reinforcement schedules induce more persistence than frequent,
43 predictable schedules,^{90,91} thus the schedule we are proposing may be optimal for promoting
44 persistence and sustained abstinence.
45

1 As women who quit smoking during pregnancy are particularly vulnerable to relapse during the
2 early postpartum, the frequency of monitoring will increase to twice per week for the initial four
3 weeks postpartum. After the first month, monitoring will be returned to the weekly, quasi-
4 random prompted monitoring schedule for the next 8 weeks. The opportunity to earn incentives
5 will be terminated at the end of postpartum week 12, consistent with our prior and ongoing
6 trials^{45,48} thereby permitting us to compare the results of the proposed intervention to our group's
7 traditional, in person financial incentives interventions.

8

9 **Validating Videos.** Key personnel will validate participant videos daily during the workweek.
10 After logging in, the process takes less than ten minutes per video. To be considered valid, the

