4 Regarding the cost-effectiveness analysis, we will employ the Brief Drug Abuse Treatment Cost
5 Analysis Program (Brief DATCAP;^{98,99}) to estimate the cost of delivering the Incentives versus
6 Best Practices smoking cessation treatments. More specifically, we will derive the direct and
7 indirect economic cost of treatment by allocating fixed costs based upon the proportion of time
8 spent delivering these programs, as well as costs that vary by patient engagement and smoking
9 status (e.g., staff time validating breath CO samples, quit-line staff time, incentives).

10 Administration costs (e.g., postage/courier service to mail participants CO monitors) will also be
11 included. Costs will be in USD for price year 2021/2022. The time period of the cost analysis
12 will span from intake to discontinuation or completion of the program. However, since the
13 duration of treatment will vary according to where in the pregnancy a woman enters the study,
14 the economic cost per person per week will also be calculated. Research-specific resources
15 consumed over the course of the study will be excluded from the cost-effectiveness analysis.

16
17 **Examining Acceptability.** At the 24-week postpartum assessment or shortly thereafter,
18 participants in both the best practices plus incentives condition and best practices control
19 condition will complete a Treatment Acceptability Questionnaire (TAQ) comparable to those
20 administered in other financial incentives interventions,²¹ including research conducted by Dr.
21 [name].^{61,64} The measure will be administered on REDCap and will query participants about the
22 ease of use, helpfulness, and convenience of the intervention, as well as whether the intervention
23 was fair, fun, and whether they would recommend it. All responses will be made using a 100-
24 point visual analogue scale. Participants in the best practices plus incentives condition will
25 receive additional TAQ questions inquiring about whether they liked self-monitoring their breath
26 CO levels, liked the incentives, and whether the incentives were helpful in terms of promoting
27 smoking abstinence during treatment and sustaining abstinence following treatment withdrawal.

28 In addition, research staff will call all participants upon completing the 24-week
29 assessment/TAQ to query them about barriers and facilitators of treatment engagement

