14 collected postpartum. Comparisons of treatment conditions on dichotomous outcomes (e.g., %
15 breastfeeding) will parallel categorical analyses for point prevalence abstinence using PROC
16 GENMOD to adjust potential covariate effects. The significance criterion will be set at alpha =
17 0.05 for all analyses.

18
19 Regarding the cost-effectiveness analysis (CEA), the CEA will be conducted by dividing the
20 average (mean) difference in treatment costs across the best practices plus incentives versus best
21 practices conditions by the average (mean) difference in abstinence rates in late pregnancy to
22 derive incremental cost-effectiveness ratios (ICERs).¹⁰¹ Statistical significance of these ICERs
23 will be determined probabilistically by employing non-parametric bootstrapped standard
24 errors.¹⁰² The main objective of this preliminary CEA will be to establish methods for obtaining
25 and analyzing data that pertain to treatment delivery in remote financial incentives interventions.
26 This basic CEA data will provide important preliminary data for a future RO1 application in
27 which we may propose conducting a more sophisticated cost-effectiveness analysis.

28
29 Regarding the acceptability data, TAQ items administered using a 100-point VAS will be
30 compared across the two treatment conditions using ANOVA's. Again characteristics that differ
31 across treatment condition will be considered as potential covariates. Responses to the semi-
32 structured interview questions will be analyzed afterwards using a thematic content
33 analysis.^{103,104} We will employ an inductive approach whereby the content of these qualitative
34 data will direct the coding and theme development. Coding of the data will involve grouping,
35 sorting, and identifying themes that reflect barriers and facilitators of treatment engagement.
36 Two researchers will perform the content analysis independently and sort responses into themes.
37 Disagreements will be resolved through discussion until consensus is reached. Those themes
38 that emerge and reflect modifiable aspects of the intervention (e.g., provision of technical
39 support, appropriateness of staff counseling and feedback surrounding quitting smoking) will be
40 taken into account in designing future iterations of this intervention that are more responsive to
41 participant's preferences.

42
43 As our examination of the intervention among the proposed subgroup of Alaska Native women

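### The ICER significance test uses a bootstrapped standard error of a ratio that is undefined in some resamples and unstable at 30 per arm; secondarily, the ratio's cost and effect periods differ without comment

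*Combined protocol and SAP*

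**What the plan says.** Under Statistical Methods, the ICER is the mean between-arm difference in treatment cost divided by the difference in late-pregnancy abstinence: the plan divides costs across the incentives and best "practices conditions by the average (mean) difference in abstinence rates in late pregnancy to" obtain the ratio. Its significance "will be determined probabilistically by employing non-parametric bootstrapped standard" errors. Alpha is 0.05 for all analyses.

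The cost period is set elsewhere, at the end of Assessment Battery. It "will span from intake to discontinuation or completion of the program. However, since the" length of treatment varies between women, cost per person per week is also planned. Costs include items that depend on engagement and smoking "status (e.g., staff time validating breath CO samples, quit-line staff time, incentives"). Under Best Practices plus Financial Incentives, the chance to earn incentives "will be terminated at the end of postpartum week 12, consistent with our prior and ongoing" trials. For a woman who completes the programme, cost therefore runs to 12 weeks postpartum.

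The plan limits its own ambition: "The main objective of this preliminary CEA will be to establish methods for obtaining" and analysing such data, ahead of a future application in "which we may propose conducting a more sophisticated cost-effectiveness analysis".

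**The concern.** A bootstrap standard error summarises an estimate well when the estimate varies smoothly over resamples. An ICER does not. If a resample has equal abstinence in the two arms, the ratio has no value. If the difference is one or two women, the ratio is very large and can change sign. With 30 per arm these resamples are not negligible, so the standard error depends on how they are handled and on the random seed. A ratio of cost to effect also has no natural null value, and the plan names none.

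Cost-effectiveness is part of Aim 1 and of the primary objective, and this analysis is meant to set methods for later use. As written, the same data could be reported as a significant or a non-significant ICER, depending on choices that the plan leaves open.

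The second issue is one of reading. All postpartum spending falls after the effect is measured, whether late pregnancy means 28 weeks (Assessment Procedures), 28 weeks or later (summary and Inclusion/Exclusion Criteria) or the end of pregnancy (Statistical Methods). A reader could take the whole-programme cost for the cost of obtaining abstinence by late pregnancy.

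**Working it through.** The plan states no ICER, standard error or threshold, so there is no figure of its own to reproduce.

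**Inputs.** 30 per arm (opening summary). Pilot late-pregnancy abstinence about 37% and 11% (opening summary). Incentives start at $6.25, rise by $1.00 per consecutive negative sample and stop at $33.25; the stated maximum is $1,620 (Best Practices plus Financial Incentives). Postpartum samples: 2 per week for 4 weeks and 1 per week for 8 weeks.

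**Bootstrap of the ratio.** Let x and y be resampled abstainers in the incentives and control arms, independent binomials with n = 30 at the observed rates. Two stylised cost models bracket the problem:
- cost difference proportional to incentive-arm quitters, so the ratio is x/(x − y) up to scale. This is nearer the plan, where costs vary with smoking status;
- cost difference constant, so the ratio is 1/(x − y) up to scale. This is a limiting case.

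Other woman-to-woman cost variation is ignored. Resamples with x = y are dropped, which is itself a rule that the plan does not give. The sums are exact.

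| Observed | Zero or negative x − y | ICER/SE, proportional | ICER/SE, constant |
|---|---|---|---|
| 11/30 vs 3/30 | 0.5% + 0.3% = 0.8% | 1.375/0.793 = 1.73 | 0.125/0.128 = 0.98 |
| 7/30 vs 3/30 (assumed smaller effect) | 5.2% + 5.5% = 10.7% | 1.75/1.672 = 1.05 | 0.25/0.349 = 0.72 |

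In the first row the Cochran-Mantel-Haenszel (CMH) p-value for abstinence is 0.015. Resamples with x and y one or two apart are 3.3% of those defined, yet supply 76% (proportional) or 78% (constant) of the variance.

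Sensitivity to unstated choices:
- Dropping negative as well as zero resamples moves the first row to 1.92 and 1.08, and the second to 1.46 and 1.02.
- With 1,000 resamples, the seed alone moves the 1.73 over roughly 1.44 to 2.16 (95% range), above 1.96 in 14% of seeds. With 10,000 resamples the range is 1.63 to 1.85.

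**Two possible readings of the rule, over repeated trials at 37% vs 11%.** Reading A calls the ICER significant if ICER/SE > 1.96. Reading B does so if at most 2.5% of resamples have an effect difference at or below zero. Both are assumed.

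| | Proportional | Constant |
|---|---|---|
| CMH significant | 68% | 68% |
| Reading A met | 43% | 18% |
| Reading B met | 66% | 66% |
| A and B disagree | 23% | 48% |

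Trials with no control abstainers (3%) have zero SE under proportional cost and are counted as meeting A; counted the other way, 43% becomes 40%.

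**Cost period.** Postpartum samples: 4 × 2 + 8 × 1 = 16. A continuous abstainer has reached the plateau by then, so they are worth 16 × $33.25 = $532. Against the stated maximum, 532/1,620 = 33%.

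For a quit date at 25 weeks with delivery at 40 weeks (assumed), there are 14 + 10 + 9 = 33 samples before delivery and 49 in all. The first 28 are worth 28 × (6.25 + 33.25)/2 = $553 and the other 21 are worth 21 × $33.25 = $698.25, which totals $1,251.25. The share is 532/1,251.25 = 43%.

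The effect on the ICER depends on how many late-pregnancy abstainers stay abstinent, which is unknown. If a fraction f earn the $532 in full and nobody else earns any of it, the addition is 0.37 × f × 532/0.26: $189, $379 or $757 for f = 0.25, 0.5 or 1. Staff time is extra and unpriced in the documents.

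**The case against.** The best defence is that the analysis is expressly preliminary, that the plan speaks of a probabilistic determination and fixes alpha, and that a resample-proportion reading would follow CMH closely: it calls only 2.6% of CMH-significant trials non-significant. At the pilot rates even the interval of ICER ± 1.96 SE covers acceptably (92–95%). The constant-cost figures sit poorly with a plan whose costs vary by smoking status, and the 7/30 versus 3/30 case is not from the documents. Net benefit also needs a willingness-to-pay range that no section supplies.

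Most of this stands, and it is why the point is minor and the proportional figures are the ones to rely on. It does not remove the problem. The plan's words, standard errors, fit the ratio-to-SE reading better, and under that reading 36% of CMH-significant trials would be labelled non-significant even with proportional cost.

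On the cost period, a reader might infer that the plan conceals a mismatch or that the ratio is invalid. The documents support neither. Both periods are stated openly, women who discontinue are costed only to discontinuation, and cost per person per week shows that duration was considered. Whole-programme cost per late-pregnancy abstainer is a legitimate quantity. Women see the earnings schedule at orientation, so later payments may partly motivate earlier abstinence. What is missing is a label and a ratio whose cost and effect periods match.

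**Conclusion.** The point holds at minor severity. The planned test has no defined value without a rule for zero differences, and at 30 per arm it is unstable: ICER/SE is about 1.7 at near-pilot results under the more plausible cost model (1.0 in the constant-cost limit), although abstinence itself has p = 0.015. Two defensible readings would disagree in 23% of trials at the pilot rates, or 48% with constant cost. These figures rest on stylised costs, on dropping zero differences and on assumed decision rules; the zero-or-negative frequencies do not depend on the cost model.

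The period difference is secondary: up to $532 of incentives, 33% of the stated maximum, or 43% for a quit date at 25 weeks with delivery at 40 weeks.

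A reader might infer that the trial's efficacy result is in doubt. It is not: the abstinence comparisons are specified separately and do not use the ICER.

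**What to change.** (a) In Statistical Methods, drop the standard-error significance test of the ICER. Resample women within arm, keeping each woman's cost and abstinence together, and summarise the resulting pairs of cost difference and effect difference by the cost-effectiveness plane, incremental net benefit with a percentile interval, and an acceptability curve over a stated willingness-to-pay range. State the number of resamples. These summaries stay defined when the effect difference is zero or negative. In the same stylised calculations the net-benefit interval covered 93–94% at 37% vs 11% and 92–94% at an assumed 20% vs 11%, where the SE interval covered 82–88%.

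(b) Label the planned ratio as whole-programme cost per additional late-pregnancy abstainer. Add whole-programme cost per additional woman abstinent at 12 weeks postpartum, where incentives end. A 24-week version may be shown as a labelled measure of durability, not as a matched ratio.

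The cost is a few sentences and some further analysis. No new data are needed, since abstinence at 12 and 24 weeks is already assessed. The one real choice is the willingness-to-pay range, which should be shown openly because the documents offer no value.
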